### Protocol Revision History

Revision Version:	Revision Date:	Revision Summary:
-------------------	----------------	-------------------

Page 3 of 49

Version 4.0:  
Revision Date: April 27th, 2022

Copyright© April 2022 Tulane University School of Medicine, Academic Research Organization on behalf of the Principal Investigator.  
All rights reserved.

TULANE UNIVERSITY  
Academic Research Organization

V1	December 8 th , 2020	
V2	April 17 th , 2021	Protocol modified for clarity
V3	July 6 th , 2021	
Section: Exclusion Criteria- updated and modified for clarity
 
Section: Added participant replacement language
 
Section: Equal Opportunity participation section added
 
Section: ECG Check device- removed
 
Section: Questionnaire- addition of AFSS
 
Section: IMP and Matching Placebo section added
 
Section: Concomitant section added
 
Section: IP/Placebo kits: updated and modified dispensation of kits for clarity
 
Section: Study schedule change, timeline of measure and participant visits
 
Section: Data sharing, Data Safety, Data Integrity Monitoring section added
 
Sections: FDA, Study Training and Monitoring, ClinicalTrials.gov and Study records access and retention added to protocol
 
Appendices: Placebo composition, CMR protocol and Abbreviated Investigational Medicine Product Insert added

V4	April 27th, 2022	
Section: Inclusion Criteria- updated and modified for clarity
 
Section: Exclusion Criteria- updated and modified for clarity
 
Section: Enrollment period criteria modified
 
Section: Labs- updated and modified for clarity
 
Section: IMP Safety Considerations- updated and modified
 
Section: IMP and Matching Placebo: Administration- modified for clarity
 
Section: IMP and Matching Placebo: Accountability- updated and modified for clarity
 
Section: Tulane University trial information record retention updated
 
Section: Preventice-updated and modified for clarity.
 
Section: In between monitoring section added
 
Section: Consent- electronic re-consent
 
Section: Study Schedule- updated timeframes, removed X-ray
 
Section: Study Design-clarified single blinded trial
 
Section: AFSS&AFEQT Questionnaires: updated and modified for clarity
 
Section: AE/SAE/UP- updated and modified for clarity
 
Section: Definition of trial outcome using ECG device- modified
 
Section: 3&12-month visit- updated
 
Section: EoT visit- updated and modified for clarity
 
Section: Steering Committee- updated
 
Section: EDC- inserted name (Dacima)
 
Section: DCC- amended name (Tulane University School of Medicine, Academic Research Organization (ARO)
 
Section: Statistical Methods, Data Analysis, and Interpretation, Part E removed
 
Section: Appendix B- updated and modified for clarity

Page 4 of 49

Version 4.0:  
Revision Date: April 27th, 2022

Copyright© April 2022 Tulane University School of Medicine, Academic Research Organization on behalf of the Principal Investigator.  
All rights reserved.

TULANE UNIVERSITY  
Academic Research Organization

## **Statement of Compliance**

---

### *International Conference on Harmonization Good Clinical Practice (ICH GCP)*

The clinical trial will be carried out in accordance with the International Conference on Harmonisation Good Clinical Practice (ICH GCP) and the following:

- United States (US) Code of Federal Regulations (CFR) applicable to clinical studies (45 CFR Part 46, 21 CFR Part 50, 21 CFR Part 56, 21 CFR Part 312, and/or 21 CFR Part 812)

The protocol, informed consent form(s), recruitment materials, and all participant materials will be submitted to the Institutional Review Board (IRB) for review and approval. Approval of both the protocol and the consent forms must be obtained before any patient is enrolled. Any amendment to the protocol will require review and approval by the IRB before the changes are implemented into the trial.

In addition, all changes to the consent form will be IRB-approved. The IRB will determine whether a new informed consent form (ICF) needs to be obtained from study participants who provided consent using a previously approved consent form.

### *Health Insurance Portability and Accountability Act (HIPAA)*

HIPAA is a federal law that required the creation of national standards to protect sensitive patient health information from being disclosed without the patient's consent or knowledge. All study procedures, data sharing, and data disclosures will be conducted in accordance with HIPAA and, therefore, should be HIPAA compliant.

## **Background**

---

 US Center for Disease Control (2018). Health Insurance Portability and Accountability Act of 1996. Retrieved on March 17, 2021, from [www.cdc.gov/phlp/publications/topic/hipaa.html](http://www.cdc.gov/phlp/publications/topic/hipaa.html).

Atrial fibrillation (AF) is the most commonly diagnosed cardiac arrhythmia in the cardiology setting. In addition to its severe impact on quality of life (QoL), AF significantly increases the risk of stroke, heart failure, and mortality. Treating AF continues to be a challenge. While AF-related symptoms and stroke risk can be managed using; rate control strategies and anticoagulation, restoration and maintenance of the sinus rhythm are deemed essential to optimize exercise capacity, QoL and stroke prevention. The CAPTAF trial demonstrated that a greater improvement in QoL was directly related to a greater reduction in AF burden in the ablation group compared to the antiarrhythmic drugs (AADs) group. AF burden has been broadly used to describe the total time (%) a patient is in AF whilst being monitored. In the TRENDS and ASSERT clinical trials, cardioembolic stroke risk strongly correlated with the duration of AF burden. Therefore, AF recurrence and burden constitute an important therapeutic target in AF patients with atrial fibrillation. Over the last 20 years, catheter-based AF ablation procedures have been widely adopted as multiple clinical trials continue to highlight its efficacy in reducing AF recurrence and burden and in improving QoL.

In trials reporting on an arrhythmia-free survival after catheter ablation, AADs were stopped after the initial 90-days of blanking period. The blanking period is a 3-month period post-ablation, where signs of early tachyarrhythmias due to the inflammatory nature of the procedure may be seen in some patients. This may provide predictive evidence that late tachyarrhythmias could develop and suggest failure in ablation. However, no significant evidence has been found and guidelines suggest against re-ablation during this window period. A recently published randomized controlled trial (POWDER-AF) evaluated whether continued use of previously ineffective AADs beyond the blanking period reduces arrhythmia recurrence after catheter ablation. This trial showed that in patients who were free of AF during the blanking period and continued the use of their AAD ablation had significantly less tachyarrhythmia recurrences as compared to patients who stopped their drug therapy altogether in a 12-month follow up after randomization. This observation might be explained by the possible influence of specific AADs on the atrial arrhythmogenic substrate, reducing the initiation and triggering of AF.

Left atrial (LA) fibrosis quantified through Delayed Enhanced Cardiac Magnetic Resonance Imaging (DE-MRI) represents a clinically effective tool for assessing the extent of atrial arrhythmogenic substrate. It has been shown to be a significant predictor of AF ablation success and major cardiovascular and cerebrovascular events in AF patients. [name] et al. characterized the severity of AF patients' fibrosis using Utah Stage 1-4 classification. [stage I (<10%), stage II (10-20%), stage III (20-30%) and stage IV (>30%)]. They reported a 6% AF recurrence risk post-ablation for every 1% increase in LA fibrosis from baseline values. Therefore, new fibrosis formation appears to be a novel marker of long-term ablation procedure outcomes. The generation of new fibrosis occurring post-ablation has also been associated with a significantly higher risk of atrial arrhythmia recurrence. Kheirkhahan's study also provides evidence that a 1% increase in fibrosis post-ablation increases the risk of AF recurrence by 3%.

A greater volume of new fibrosis ( $\geq 21\%$ ) corresponded with a lower arrhythmia-free survival. In addition to being a significant predictor of AF recurrence, a higher fibrotic burden strongly correlated with a higher risk of stroke (Figure 1), heart failure and mortality in AF patients across multiple studies.

King et al. conducted a 5-year study based on follow-up data from 1,233 patients to quantify LA fibrosis via Late-Gadolinium Enhancement MRI (LGE-MRI).

The study showed atrial fibrosis to be a strong predictor of major cardiovascular and cerebrovascular events. Patients with LA fibrosis stage IV had a 67% increased risk compared to patients with stage I of

the disease. Akoum et al. demonstrated that atrial fibrosis is independently associated with appendage thrombus and spontaneous contrast. Fibrosis is also shown to reduce LA appendage velocity, which is also associated with an increased risk of stroke. In conclusion, progression of fibrosis post-ablation was associated with worse outcomes. For this reason, regarding long-term management of AF, it would be appropriate to look for new therapeutic options that can target a reduction in the progression of fibrosis in order to promote positive outcomes and optimize disease management.

Dronedarone is an anti-arrhythmic drug with properties belonging to Vaughan-Williams class I-IV. It has a similar structure to amiodarone (Class III AAD) and is effective in reducing AF recurrence, AF burden and cardiovascular hospitalization rates in both placebo-controlled trials and in real-world studies. Dronedarone exerts antiarrhythmic effects by inhibiting the outward K1 currents and increasing the refractory period. Additionally, data from multiple prospective observational studies suggest dronedarone may improve QoL. Dronedarone seems to have a reasonable safety profile, with fewer non-cardiovascular risks and a lower risk of ventricular pro-arrhythmia compared to other AADs.

Based on our preliminary data, dronedarone appears to have the potential to slow down the progression of cardiac fibrosis, with multiple mechanisms of action hypothesized. One of the main speculated mechanisms of action has been derived from pre-clinical publications and is based on dronedarone preventing vascular alterations that participate in structural remodeling and atrial maintenance substrate. Oxidative stress (ROS) generated in the myocardium promotes endothelial to mesenchymal transition (EndMT) by reducing endothelial nitric oxide (NO) production. Numerous studies have shown that ROS and EndMT are major contributors towards cardiac fibrosis. Circulating symmetric dimethylarginine (SDMA), a biomarker that reduces the synthesis of NO, is also associated with increase in atrial wall thickness in AF. Dronedarone stimulates nitric oxide synthase (NOS) which increases the bioavailability of NO, and reduces SDMA, playing a critical role in preserving the epithelial phenotype. In fact, there is an improvement in global antioxidant status after treatment with dronedarone.

Furthermore, a decrease in collagen deposition in the atria has been observed after treatment with dronedarone, thereby improving atrial structure, decreasing wall thickness, and slowing down the development of cardiac fibrosis. Finally, during episodes of AF, factors known to induce atrial fibrosis growth such as, collagen-1 and fibronectin-1, are released into atrial tissues. For this reason, rhythm control by means of AADs Class III may serve to limit the amount of time available for these biomarkers to disperse into atrial tissues as well as, proactively managing fibrosis progression.

[figure not shown]
[figure not shown]
Preliminary data from [name] team at the University of Utah (Salt Lake City, UT) assessing fibrosis progression in AF patients (n = 17) that received standard of care (SOC) (n = 8) or dronedarone (Multaq®, n=9), are presented in Figure 2. Patients underwent two MRIs over

Page 10 of 49

Version 4.0:  
Revision Date: April 27th, 2022

Copyright© April 2022 Tulane University School of Medicine,  
All rights reserved

**Figure 1:** Cumulative incidence of stroke by Utah Stage of LA fibrosis. Adapted from King et al.

**Figure 2:** Mean fibrosis at baseline and follow-up by randomized treatment group. Preliminary data from the University of Utah.

TULANE  
University  
Arch Organization

the course of a median 365.5 days [IQR: 290-382] as part of their care. In the SOC group, they observed a 10% progression of fibrosis, whereas in the dronedarone group, there was only a 4.5% progression over this period. Dronedarone slowed atrial fibrosis progression by more than 50% relative to the SOC group. This reduction is clinically relevant, as each 1% increase in atrial fibrosis from baseline is associated with a 6% higher risk of AF recurrence after ablation. Although underpowered due to the small sample size, a trend is apparent between baseline and follow-up MRIs, and it appears as though vast differences exist. With an increased sample size, we may see more significant effects.

## **Purpose and Objectives**

---

### *Purpose*

Determine whether dronedarone is effective in slowing the progression of fibrosis and decreasing atrial arrhythmia (AA) recurrence (atrial fibrillation, atrial flutter, or atrial tachycardia) in patients who have undergone AF ablation therapy.

### *Aims*

**Aim 1:** Determine if dronedarone reduces post-ablation incidences of atrial arrhythmia recurrence compared to placebo.

**Aim 2:** Determine whether dronedarone is effective in slowing down the progression of fibrosis after ablation compared to SOC alone.

## **Study Design**

---

EDORA is a multicenter, prospective, phase IV, randomized, and single-blinded clinical trial.

Patients with AF undergoing ablation will be stratified by age (>65 years and <65 years) and type of atrial fibrillation (paroxysmal and persistent). Upon stratification and ablation, they will be randomized to one of two trial groups. They will either receive dronedarone (i.e. Multaq®) 400mg BID (treatment group) or placebo (control group). The control group will be started on placebo and physicians will be advised to limit the initiation of AADs to essential cases only, avoiding amiodarone and dronedarone.

Each patient will receive a pre-ablation CMR scan to assess the extent of atrial fibrosis present, followed by scans at 3 and 12-month post-ablation. QoL changes will be evaluated from baseline and again at 3 months and 12-months via the AF Effect on QualiTy of life (AFEQT) questionnaire form. frequency, duration, and severity of an AF episode, if present will be evaluated from baseline and again at 3 months and 12-months via the Atrial Fibrillation Severity Scale (AFSS) questionnaire form.

Patients will be followed post-ablation for AA recurrence (atrial fibrillation, atrial flutter, or atrial tachycardia) and will receive continuous ECG monitoring via a 30-day ECG wearable monitoring device starting at discharge, then again at 3, 6, 9- and 12-months post-ablation. Patients will also be encouraged to use any personal devices that provide ECG readings (e.g. smartwatch, etc.) in between the study timepoints and to share this data with the corresponding research team.

Phone calls or study visits will be scheduled at the study participants' 6- and 9-month mark to assess for medication compliance, changes to their medical histories, medication history, and adverse event

Page 11 of 49

Version 4.0:  
Revision Date: April 27th, 2022

Copyright© April 2022 Tulane University School of Medicine, Academic Research Organization on behalf of the Principal Investigator.  
All rights reserved.

TULANE UNIVERSITY  
Academic Research Organization

reporting as well as to assess that all study devices are working accordingly. Evaluation as to whether a patient has reached any trial endpoints will also be analyzed at this time.

Physicians will be advised to avoid adjustments in drug therapy unless absolutely necessary (severely symptomatic patients, patients with newly diagnosed heart failure, New York Heart Association (NYHA) Class IV, etc.). Severely symptomatic patients will be defined as, study participants with non-tolerated palpitations or chest pain, dizziness, syncope, dyspnea, severe fatigue, or suddenly reduced ability to exercise.

Any initiation or change of an antiarrhythmic treatment in the treatment or control group will be considered as a secondary endpoint of the trial. Patients will continue to be monitored for fibrosis progression and AF burden via CMR scans and ECG monitoring device until the end of the follow-up period. In the case of AA recurrence after ablation, AAD initiation or change will be left to the discretion of the treating physician.

### *Post-trial Care*

The long-term care of the patient will remain the responsibility of their primary treating physician and clinical care team.

## **Study Endpoints**

---

### *Primary Endpoints*

The primary endpoints of the study are defined as the first occurrence of AA (i.e. atrial fibrillation, atrial flutter, or atrial tachycardia) post-ablation and the progression of atrial fibrosis post-ablation.

#### **1) Post-ablation AA recurrence**

Monitoring will start upon discharge, usually 24-48 hours after AF ablation.

Defined as:

- a) Time to first AA episode lasting > 30 continuous seconds, after cardiac ablation (including tachyarrhythmias presented during the 90-day post ablation blanking period).

This will be recorded by either the occurrence of a single positive AA ECG reading on the BodyGuardian® MINI Plus EL ECG monitoring study device, a 12-lead ECG, Holter monitor, or other ECG monitoring device. If there are technical difficulties or accessibility issues using the study device, patients can be monitored for AA throughout the trial via a 12-lead ECG or other heart monitoring device if necessary.

- b) New AAD initiation for AF recurrence after AF ablation, including initiation of the treatment during the blanking period, or with no available positive ECG reading.

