### *Definition of Trial Outcome using ECG Device*

The trial outcome is defined by at least one ECG tracing indicating AA for >30 seconds. AA demonstrated by any ECG device can include AA occurrence during the 90-day blanking period.

If a repeat ablation is performed, but there is no AA recurrence demonstrated by ECG readings from SOC ECG device or any other ECG device, AA recurrence will be inferred for the purposes of the primary study analysis and assigned to the date of the repeat ablation.

Page 24 of 49

Version 4.0:  
Revision Date: April 27th, 2022

Copyright© April 2022 Tulane University School of Medicine, Academic Research Organization on behalf of the Principal Investigator.  
All rights reserved.

TULANE UNIVERSITY  
Academic Research Organization

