#### ***Atrial Arrhythmia (AA) Recurrence***

The rate limiting factor in the required sample size is AA recurrence (atrial fibrillation, atrial flutter, atrial tachycardia). AA recurrence is defined as a one instance, continuous >30 second strip reading on either 12-lead ECG, Holter monitor or study devices (including during the blanking period)

AA recurrence will be based on the following assumptions:

- 50% of patients in the control group will have AA recurrence in 1-year, post-ablation (including during the blanking period) and,
- the relative reduction of AF recurrence will be by 33% in the dronedarone group compared to the control group and,
- 20% of subjects could be lost during the follow-up periods and,
- 2-sided  $\alpha=0.05$ .

The EDORA trial will have a total of 330 patients participating, thus, 165 in each trial arm. Therefore, a calculated total of 138 AF recurrences will have 86% power to detect the group differences.

The study will be defined as successful if the hypotheses for both co-primary endpoints are positive, i.e., rejecting the null hypothesis. Therefore, in terms of overall type I error of the study, the sample size calculation does not need to adjust for the multiplicity. However, the type II error, i.e., the power for each individual test needs to be adjusted in this case to achieve the overall power of the study. For the endpoint of atrial fibrosis progression, given that 330 patients will be recruited, we have almost 100% power to detect the expected difference. For AF recurrence, the study will have at least 85% power. Therefore, for the two co-primary endpoints, the study will have at least 85% overall power for a positive outcome, i.e., the study is powered to detect the difference in both atrial fibrosis progression and AF recurrence between the two arms.

Most studies evaluating the effects of AAD after ablation started their monitoring after the 3-month blanking period. Our trial will start assessing for the primary endpoint of AF recurrence on the day of discharge, and so we expect a significantly higher event rate. A few recent studies reporting recurrence data during the first three months after ablation such as, the AMIO-CAT study showed a 53% AF recurrence rate after ablation in a placebo group and AF recurrence at 6 months was 48%. In the EAST-AF study, randomizing paroxysmal and persistent AF patients to short term AAD use vs control, the rate

Page 34 of 49

Version 4.0:  
Revision Date: April 27th, 2022

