## C. Analysis of the co-primary endpoints

### *Analysis of AF Recurrence*

Time-to-event-analysis will be conducted for AF recurrence. Patients with unobserved AF events during the study trial due to loss-of-follow-up/death or termination of the study will be treated as censored and the time to first AF recurrence will be treated as the outcome. Cumulative AF rates will be calculated by intervention conditions using the Kaplan-Meier (KM) method and compared using the log-rank test. Stratified KM curves will also be performed by Utah Stages at baseline (separate strata for Utah stages I - II, and III - IV) to investigate if the treatment effects vary across different stages. Cox proportional hazards models will be used to assess the intervention effects on the time to AF recurrence after discharge from the procedure. The proportional hazards assumption will be tested by means of graphical methods and statistical tests of lack of fit.

Due to the nature of the randomization in the study design, it is expected that the demographic characteristics and other important clinical factors will be balanced between the two groups. However, in addition to the primary predictor and the intervention condition, potential confounders will also be included in the model.

Due to the clustering effects at a physician level, we will include random effects of the physician in the model. We will also further investigate if the intervention effects are similar across the stages after controlling potential confounding effects by including the interaction of the intervention and the Utah stage in the models. In all the models, the estimated hazard ratio between the treatment and control groups with its 95% confidence interval will be provided.

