### *Analysis of LA Fibrosis Progression*

The primary outcome variable will be changes in the percentage of fibrosis from baseline, 3- and 12-months via CMR assessments in patients randomized to receive dronedarone vs. placebo.

We will apply models for longitudinal data to analyze the LA fibrosis progression over the follow-up period. The two most popular approaches for longitudinal data are the Linear Mixed-effects Model approach (LMM) and Generalized Estimating Equations (GEE). The LMM requires parametric assumption such as, normality on the random effects and model errors, and it is more powerful when the assumptions are met, but vulnerable to departures from the assumed distributions. GEE provides robust

estimates because it does not require any distribution assumption. Therefore, we will first investigate the distribution of the outcome, and if the distribution assumption is reasonable, we will use LMM model, otherwise, we will use GEE approach. Due to the clustering effect at a physician level, we will use random effects in LMM or working correlation in GEE model to account for the correlations. In all the models, the primary predictor is the intervention condition. We will also consider controlling other potential confounders if the data exhibits any. The intervention effect is assessed by the estimated coefficient of the primary predictor. The coefficient with right direction and a p value  $<0.05$  indicates there is a significant intervention effect.

Per standard principles, the primary analyses will be done on an intention to treat basis (ITT), treating all randomized patients with available outcome data regardless of compliance. A Robustness Analysis will include a per protocol analysis, where only those patients who actually received their assigned treatment (e.g., those who received dronedarone per the dosing protocol) will be analyzed. In terms of missing data, the survival analysis approach to the AF recurrence outcome will censor any patients who drop out of the study without AF recurrence at the time of their last known contact. While we would propose such patients to have their first documented recurrence date counted as their failure date, alternative analysis approaches for the analysis of interval-censored data will also be considered for robustness.

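### The atrial arrhythmia co-primary event is a composite in the endpoint sections but ECG-only in the sample size section, the analysis section does not say which applies, and the stated power omits the assumed 20% loss

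*Combined protocol and SAP*

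**What the plan says.** The AA event is described in four places.

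- **Primary Endpoints, Post-ablation AA recurrence.** Part (a) is an AA episode of more than 30 seconds on any ECG device, blanking period included. Part (b) adds a new AAD started for AF recurrence, "including initiation of the treatment during the blanking period, or with no available positive ECG reading". Repeat ablation is not listed.
- **Definition of Trial Outcome using ECG Device.** One tracing of more than 30 seconds is an event. After a repeat ablation with no tracing, "AA recurrence will be inferred for the purposes of the primary study analysis and assigned to the date of the repeat ablation". AAD start is not listed.
- **Sample Size Estimation, Atrial Arrhythmia (AA) Recurrence.** "AA recurrence is defined as a one instance, continuous >30 second strip reading on either 12-lead ECG, Holter monitor or study devices". Neither AAD start nor repeat ablation is listed. The power claim follows: "a calculated total of 138 AF recurrences will have 86% power to detect the group differences". One of the stated assumptions is that "20% of subjects could be lost during the follow-up periods".
- **Analysis of AF Recurrence.** "the time to first AF recurrence will be treated as the outcome". There is no definition or cross-reference, and the text says AF although the endpoint covers AF, flutter and atrial tachycardia.

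The missing-data text under Analysis of LA Fibrosis Progression would have certain patients take "their first documented recurrence date counted as their failure date", which does not help when there is no tracing. Study Design adds: "Any initiation or change of an antiarrhythmic treatment in the treatment or control group will be considered as a secondary endpoint of the trial". Repeat ablation is also on the secondary list.

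Study Design leaves AAD decisions after recurrence to the treating physician, and the Control Group section repeats this for placebo. The Blinding section says that site investigators are unblinded and may be treating the participant. It describes blinded reading for ECG and CMR only.

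**The concern.** Take a patient who starts a new AAD for suspected recurrence, or has a repeat ablation, with no positive tracing from any device. Under the endpoint sections this patient is an event. Under the sample size definition the patient is censored. The analysis section does not choose, so two competent analysts could report different hazard ratios from the same data. The success rule requires both co-primary endpoints to be positive, so the AA result can decide the trial. The Blinding section also allows data analysts access to arm information when required, so a choice made late could be data-driven.

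Two further consequences follow. Under the composite, part of the result rests on decisions by physicians who may know the arm. And the events and power were worked out for the narrower definition, without the loss that the same section assumes.

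**Working it through.** **1. Event sets side by side**

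| Section | ECG >30 s | New AAD, no tracing | Repeat ablation, no tracing |
|---|---|---|---|
| Primary Endpoints | yes | yes | not listed |
| Trial Outcome using ECG Device | yes | not listed | yes |
| Sample Size, AA Recurrence | yes | not listed | not listed |
| Analysis of AF Recurrence | undefined | undefined | undefined |

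The first two rows are compatible and add up to a three-part composite. The third row is narrower and the fourth is silent.

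**2. Reproducing the plan's figure**

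Inputs from the sample size section: 165 per arm, 50% control recurrence at 1 year, 33% relative reduction, two-sided 5%.

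- Dronedarone rate: 0.50 × (1 − 0.33) = 0.335.
- Hazard ratio under proportional hazards: ln(0.665)/ln(0.50) = 0.589.
- Events: 165 × (0.50 + 0.335) = 137.8, that is 138.
- Freedman power: Φ(√138 × (1 − 0.589)/(1 + 0.589) − 1.96) = 86.0%. Schoenfeld gives 87.6% and the two-proportion formula 86.3%.

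The plan's 138 and 86% are reproduced, with all 330 patients contributing in full and none of the 20% loss removed.

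**3. Putting the 20% loss in (ECG-only, planned effect)**

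- *Losses at uniform times over the year, exponential event times.* The chance of an observed event is 0.8p + 0.2(1 − p/λ), with λ = −ln(1 − p). Control: 0.8 × 0.50 + 0.2 × (1 − 0.50/0.693) = 0.456. Dronedarone: 0.8 × 0.335 + 0.2 × (1 − 0.335/0.408) = 0.304. Events: 165 × (0.456 + 0.304) ≈ 125. Power is 82.6% (Freedman) or 84.3% (Schoenfeld). A simulated log-rank test gives 83.9%.
- *Lost patients contribute nothing.* 165 × 0.8 = 132 per arm, and 132 × 0.835 = 110 events. Power is 77.5% (Freedman), 77.9% (two proportions), 79.1% (simulated) or 79.4% (Schoenfeld). Reading 33% as exactly one third gives 80.3% (Schoenfeld).

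**4. Power under the composite**

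The documents give no rate for events without a tracing, so these rates are assumptions: 5% or 10% of ECG-event-free controls, with the same 20% loss and simulated log-rank tests.

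| Added events in the two arms | Lost contribute nothing | Uniform loss |
|---|---|---|
| Equal share of ECG-event-free patients | 70-75% | 75-80% |
| Equal in percentage points of all patients | 78% | 83% |
| Same 33% reduction as ECG events | 82-85% | 86-89% |

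Power could be lower than, similar to or higher than ECG-only.

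**5. Sensitivity to unblinded decisions (illustration only)**

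Assume no drug effect, 50% ECG recurrence in each arm, 165 per arm and no loss. The nominal false-positive rate in each direction is 2.5%.

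- Untraced events in 5% of ECG-event-free controls and 0% on drug (0.05 × 82.5 ≈ 4 extra events): 6.5% favouring dronedarone.
- 5% in controls and 10% on drug: 0.8% favouring dronedarone and 6.4% favouring placebo.

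A handful of events shifts the error rate, and the direction depends entirely on the assumed split.

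**The case against.** The best defence is that the plan has one governing definition. The Primary Endpoints section is where the endpoint is formally defined, the ECG device section adds a rule expressly for the primary analysis, and the sample size text is only a planning assumption. Much of this stands. A reader might infer three contradictory definitions, but the first two sections read naturally as additive. What does not stand is the description of the third as merely a planning figure. It states a definition, it carries the power claim, and nothing in the analysis section overrides it.

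Other strong readings also fail.

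- *AAD start has no event date.* The start date is the obvious one. It only needs writing down.
- *Secondary status removes AAD start and repeat ablation from the primary.* An outcome can be both. The secondary AAD endpoint explicitly continues after the primary event.
- *The result is biased towards dronedarone.* The advice to limit AADs covers both arms, no rates are given, and investigators only may be the treating physicians. The inflated figures above need a one-sided split that no document supports.
- *The whole trial's false-positive rate is inflated.* Fibrosis is read blinded and must also be positive. If neither drug effect exists and the tests are independent, even the more extreme assumption of 10% against 0% (13.6% for AA) gives 0.025 × 0.136 = 0.3%. That figure does not cover the case where fibrosis truly responds and AA alone decides.

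The DSMB and Steering Committee charters are not among the documents, so a blinded check of untraced events is not described here, which is different from not existing.

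On power, the missing-data text censors dropouts at last contact, which favours the uniform-loss figure. Extending follow-up to 13 months at a constant hazard, with exponential loss, would give about 131 events and 84% (Freedman) to 86% (Schoenfeld). The plan states its rate for 1 year and makes no such claim.

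**Conclusion.** The point holds in a limited form. The AA co-primary is a composite when the two endpoint sections are read together, ECG-only where events and power are derived, and unspecified, under the name AF, where it is analysed. This needs settling before any analysis by arm, because the endpoint is required for success.

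The composite itself is defensible, since a new AAD ends study treatment in both arms. Its dependence on possibly unblinded decisions is a reason for a sensitivity analysis and is not evidence of bias.

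The power shortfall is separate and exists even under ECG-only: 83-84% with uniform loss and 78-80% if lost patients contribute nothing, against the stated 86% and the claim of at least 85%. These figures rest on the plan's rates, proportional hazards and a 1-year horizon. For the composite, power is not established in either direction.

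**What to change.** 1. State one event list, either the composite of the two endpoint sections or ECG-only if the sponsor prefers. Give the event date for each component: date of the tracing, date of AAD start, date of repeat ablation. Use it identically in Primary Endpoints, Trial Outcome using ECG Device, Sample Size and Analysis of AF Recurrence, and write AA in place of AF.
2. Prespecify a sensitivity analysis on the other definition. If the composite is primary, count only AA of more than 30 seconds documented by ECG and read by the blinded core lab. If ECG-only is primary, run the composite.
3. Restate events and power at 330 patients for the chosen definition with the 20% loss included. Name the loss pattern and, for the composite, the assumed rate of untraced events.

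The choice in step 1 is a trade-off. ECG-only may miss recurrences treated between monitoring windows, where recordings are voluntary. The composite captures them but includes decisions by physicians who may know the arm.

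The cost is wording in four sections, one extra analysis and a less favourable ECG-only power figure. No additional adjudication staff and no larger enrolment are needed.
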